4.1.2. Evaluation Period

The evaluation period begins when the participant completes screening and is enrolled in the study. Assessments and procedures will be conducted as described in the SoA (Section [1.3](#)).

Participants in Part 1 will be randomized to placebo or LY3819253. The Sponsor will decide when to trigger activation of Part 2. Activation of Part 2 will be communicated to sites.

Participants in Part 2 will be assigned to a cohort as follows:

- Prevention Cohort: Participants who are SARS-CoV-2 negative during screening on the POC test will be randomized to one of three arms: placebo, LY3819253 700 mg, or LY3819253 350 mg + LY3832479 700 mg.
If enrolling to a placebo-controlled trial is challenged by an effective medication becoming available for prevention of COVID-19 and SARS-CoV-2, then the placebo arm may be dropped.

Note: It is possible that some participants have SARS-CoV-2 negative result on the screening point of care test, but could be positive on the baseline SARS-CoV-2 PCR test. The results from the baseline test will not be available until after the participant is randomized. Once positive results are known from the baseline test, these participants will be unblinded and have the option to continue to be followed for safety according to the Prevention Cohort SoA. Unblinded participants will not be included as part of the defined prevention population

The evaluation period for the Prevention Cohort is 8 weeks, with follow-up to Day 169.

- Treatment Cohort: Participants who test SARS-CoV-2 positive during screening with the POC test will be randomized to one of two arms: LY3819253 700 mg, or LY3819253 700 mg + LY3832479 1400 mg.

The evaluation period for the Treatment Cohort is 4 weeks, with follow-up to Day 85.

Participants in Part 3 will be randomized to LY3819253 700 mg or LY3819253 700 mg and LY3832479 1400 mg. The evaluation period for Part 3 is 4 weeks, with follow-up to Day 85. The Sponsor will decide when to trigger activation of Part 3. Activation of Part 3 will be communicated to sites. Part 3 may be activated prior to Part 2.

Part 2 and Part 3 could be activated concurrently. However, Part 3 will not enroll concurrently with Part 2 at the same facility.

Participants will receive one intravenous infusion of study intervention.

The maximum total duration of study participation for each participant of the prevention groups is 24 weeks. See the SOA for prevention groups in Section 1.3.1.

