POC-Negative/RT-PCR Positive	All participants in the Enrolled/ITT population in Part 2 who are SARS-CoV-2 POC negative and RT-PCR positive at baseline.
PK Analysis	All randomized participants who received study intervention and have evaluable PK sample. Participants will be analyzed according to the intervention they received.

Abbreviations: ITT = intent to treat; PK = pharmacokinetics; RT-PCR = reverse transcription – polymerase chain reaction; SARS-CoV-2 = severe acute respiratory syndrome coronavirus 2.

Throughout the document, the term “the Prevention populations” will be used to describe both the Part 1 Prevention and Part 2 Prevention populations. Analyses on the Prevention populations will be conducted on each Prevention population separately. The terms “the Treatment populations” and “the Safety populations” are defined similarly.

The following study arms are defined for the purposes of comparison:

Study Arm	Study Part	Dose	Intervention
1	Part 1	4200 mg	LY3819253
2	Part 1	---	Placebo
3	Part 2 (Prevention Cohort)	700 mg	LY3819253
4	Part 2 (Prevention Cohort)	350 mg + 700 mg	LY3819253 + LY3832479
5	Part 2 (Prevention Cohort)	---	Placebo

Study Arm	Study Part	Dose	Intervention
6	Part 2 (Treatment Cohort)	700 mg	LY3819253
7	Part 2 (Treatment Cohort)	700 mg + 1400 mg	LY3819253 + LY3832479
8	Part 3	700 mg	LY3819253
9	Part 3	700 mg + 1400 mg	LY3819253 + LY3832479

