### 5.1.2. *Evaluation Period*

The evaluation period begins when the participant completes screening and is enrolled in the study. Participants will be randomized to placebo or LY3819253 in Part 1. In Part 2, participants will be randomized to placebo, LY3819253, or LY3819253 in combination with LY3832479. In Part 3, participants will be randomized to LY3819253 or LY3819253 in combination with LY3832479. Assessments and procedures will be conducted as described in the Schedule of Activities (SoA; Section 1.3 of the protocol).

If a participant is hospitalized, efforts will be made to retrieve hospital records and report procedures and assessments according to the SoA, as feasible.

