Part 2 Prevention	
Definition: All participants in the Enrolled/Intent-to-Treat population in the Prevention Cohort in Part 2 who are SARS-CoV-2 RT-PCR negative and serology negative at baseline.
 
Purpose: Used for efficacy and health outcomes analyses.
 
Treatment Groups (Short Label): 700 mg LY3819253, 350 mg LY3819253 + 700mg LY3832479, and placebo
 
Inferential Comparisons: LY3819253 versus placebo, LY3819253 + LY3832479 versus placebo

Part 1 Treatment	
Definition: All participants in the Enrolled/Intent-to-Treat population in Part 1 who are SARS-CoV-2 RT-PCR positive at baseline and serology negative at baseline.
 
Purpose: Used for efficacy and health outcomes analyses.
 
Treatment Groups (Short Label): 4200 mg LY3819253 (4200 LY) and placebo (Pbo)
 
Inferential Comparisons: LY versus placebo

Part 2 Treatment	
Definition: All participants in the Enrolled/Intent-to-Treat population in the Treatment Cohort in Part 2 who are POC positive, RT-PCR positive, and SARS-CoV-2 serology negative at baseline.
 
Purpose: Used for efficacy and health outcomes analyses.
 
Treatment Groups (Short Label): 700 mg LY3819253, 350 mg LY3819253 + 700mg LY3832479, and placebo
 
Inferential Comparisons: LY3819253 versus placebo, LY3819253 + LY3832479 versus placebo

Part 3 Treatment	
Definition: All participants in the Enrolled/Intent-to-Treat population in Part 3 who are RT-PCR positive, and SARS-CoV-2 serology negative at baseline.
 
Purpose: Used for efficacy and health outcomes analyses.
 
Treatment Groups (Short Label): 700 mg LY3819253 and 700 mg LY3819253 + 1400mg LY3832479
 
Inferential Comparisons: LY3819253 versus LY3819253 + LY3832479 (not powered for formal inference)

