## Analysis Populations

Population	Description
Part 1 Safety	
Definition: All participants randomly assigned and who received any amount of study intervention in Part 1. Participants will be analyzed according to the intervention they actually received.
 
Purpose: Used for safety analyses.
 
Treatment Groups (Short Label): 4200 mg LY3819253 (4200 LY) and placebo (Pbo)
 
Inferential Comparisons: LY versus placebo

Part 2 Safety	
Definition: All participants randomly assigned and who received any amount of study intervention in Part 2. Participants will be analyzed according to the intervention they actually received.
 
Purpose: Used for safety analyses.
 
Treatment Groups (Short Label): 700 mg LY3819253, 350 mg LY3819253 + 700mg LY3832479, and placebo
 
Inferential Comparisons: LY3819253 versus placebo, LY3819253 + LY3832479 versus placebo

Part 3 Safety	
Definition: All participants randomly assigned and who received any amount of study intervention in Part 3. Participants will be analyzed according to the intervention they actually received.
 
Purpose: Used for safety analyses.
 
Treatment Groups (Short Label): 700 mg LY3819253 and 700 mg LY3819253 + 1400mg LY3832479
 
Inferential Comparisons: LY3819253 versus LY3819253 + LY3832479 (not powered for formal inference)

Fully Dosed	
Definition: All participants in the Safety population who receive either placebo or a complete infusion of study intervention.
 
Purpose: Used for sensitivity assessments in the event that there are patients who do not receive a complete infusion of study drug.
 
Treatment Groups (Short Label): Part 1: 4200 mg LY3819253 (4200 LY) and placebo (Pbo)
 
Part 2: 700 mg LY3819253, 350 mg LY3819253 + 700mg LY3832479, and placebo
 
Inferential Comparisons: LY versus placebo

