## 6.12. Safety Analyses

Percentages will be calculated using the Safety populations as the denominator. For events that are sex-specific, the denominator and computation of the percentage will include only participants from the given sex. In the event of differential dropout rates, additional summary tables comparing exposure-adjusted incidence rates will be generated instead of, or in addition to, percentages.

Generally, the following statistical methods will be used, unless otherwise noted:

- percentage-based analyses:
  - p-values based on Fisher's exact test, and
  - odds ratios with treatment as the numerator and placebo as the denominator
- continuous measurements (single postbaseline timepoint):
  - p-value based on ANCOVA:
    - model containing terms for treatment and the continuous covariate of baseline measurement, and
    - Type III sums of squares will be used.
- continuous measurements (multiple postbaseline timepoints):
  - p-value based on MMRM:
    - model containing terms for treatment, visit, the continuous covariate of baseline measurement, and the interactions of treatment by visit, and
    - Type III sums of squares will be used.

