### 6.12.1. Baseline and Postbaseline Definitions for Safety Groups

Table PYAD.6.7 provides conceptual definitions of baseline and postbaseline by analysis type. More specific detail for each submission is provided in an appendix, if necessary.

**Table PYAD.6.7. Baseline and Postbaseline Definitions for Safety Groups  
Initial Controlled Periods of Individual Studies  
Controlled Integrated Analysis Sets**

Analysis Type	Baseline	Postbaseline
TEAEs	Start of screening and ends prior to the study drug dose.	Starts after initiation of the study drug dose and ends on or prior to the day of study disposition
Treatment-Emergent Abnormal Laboratory Values and Vital Signs	Start of screening and ends prior to the study drug dose.  All scheduled and unscheduled measurements will be included.	Starts after initiation of the study drug dose and ends on or prior to the day of study disposition.  All scheduled and unscheduled measurements will be included.

**Baseline and Postbaseline Definitions for Safety Groups****Initial Controlled Periods of Individual Studies****Controlled Integrated Analysis Sets**

Analysis Type	Baseline	Postbaseline
Change from Last Baseline to Week xx and to Last Postbaseline for Laboratory Values and Vital Signs	Start of screening and ends prior to the study drug dose.  The last scheduled nonmissing assessment recorded prior to the date of the first dose.	Starts after initiation of the study drug dose and ends on or prior to the day of study disposition.
		Only scheduled visits will be included. The early termination visits are considered scheduled visits.

Abbreviation: TEAE = treatment-emergent adverse event.

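### The SAP's Part 2 Safety population mixes two separately randomized cohorts against a placebo group that only one of them has, and its Part 2 Treatment row specifies a placebo comparison with no placebo participants

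*SAP*

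**What the plan says.** SAP Section 6.1.1 makes the groups and comparisons in Table PYAD.6.1 the default for all analyses.

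- **Part 2 Safety row.** The population is "All participants randomly assigned and who received any amount of study intervention in Part 2", analyzed by the intervention received. It has three groups (700 mg LY3819253; 350 mg + 700 mg; placebo), and each active regimen is compared with placebo.
- **Part 2 Treatment row.** The population is limited to Treatment Cohort participants with a positive point-of-care (POC) test. The groups are nevertheless "700 mg LY3819253, 350 mg LY3819253 + 700mg LY3832479, and placebo", again with each active regimen compared with placebo.
- **SAP Section 5.1.2.** This describes one randomization: "In Part 2, participants will be randomized to placebo, LY3819253, or LY3819253 in combination with LY3832479".
- **SAP Section 6.12.** Safety percentages use the Safety populations as denominator. The contrast is "odds ratios with treatment as the numerator and placebo as the denominator", and no cohort term appears in any model.

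The protocol describes a different structure. Under Section 4.1.2, POC-negative participants are randomized among placebo, 700 mg and 350 mg + 700 mg. For the others, "Participants who test SARS-CoV-2 positive during screening with the POC test will be randomized to one of two arms", 700 mg or 700 mg + 1400 mg. Section 6.3 adds that Treatment Cohort participants are told they are not on placebo. Section 9.3 introduces its arms table with "The following study arms are defined for the purposes of comparison" and lists 700 mg twice: arm 3 (Prevention) and arm 6 (Treatment).

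**The concern.** A Part 2 Safety population without a cohort restriction, with a single 700 mg label and analysis by intervention received, puts arms 3 and 6 in one column. The comparator, arm 5, is entirely POC-negative. The contrast would lose the protection of randomization in three ways.

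- **Infection at entry.** Everyone in arm 6 tested positive at screening; nobody in arm 5 did.
- **Length of observation.** The TEAE window "Starts after initiation of the study drug dose and ends on or prior to the day of study disposition". For planned duration, "The maximum total duration of study participation for each participant of the prevention groups is 24 weeks", against 12 weeks for the treatment group.
- **Assessment schedule.** Vital signs are recorded far more often in the Prevention Cohort.

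The biases do not all point the same way, so the pooled comparison could create a false safety signal or hide a real one. Arm 7 (700 mg + 1400 mg) has no label in any Part 2 row. It would either drop out or be absorbed into the combination versus placebo contrast, which would then be confounded too.

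The Part 2 Treatment row is a separate fault: it names a comparator, and a combination dose label, that the protocol does not assign to that cohort.

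**Working it through.** **Step 1. Arm count.** The protocol synopsis states 9 arms. From Sections 4.1.2, 6.3 and 9.3: Part 1 has 2, Part 2 Prevention 3, Part 2 Treatment 2 and Part 3 2. The sum 2 + 3 + 2 + 2 = 9 agrees. SAP Table PYAD.6.1 has 2 + 3 + 2 = 7 groups. The shortfall is in Part 2, where five arms are represented by three labels.

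**Step 2. Mapping the Part 2 arms to the SAP labels.**

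| Protocol arm | Cohort | SAP Part 2 Safety label |
|---|---|---|
| 3: 700 mg | Prevention | 700 mg |
| 4: 350 + 700 mg | Prevention | 350 + 700 mg |
| 5: placebo | Prevention | placebo |
| 6: 700 mg | Treatment | 700 mg (same label as arm 3) |
| 7: 700 + 1400 mg | Treatment | none |

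The Part 2 Treatment population can draw only on arms 6 and 7, so it has no placebo participants and no 350 + 700 mg participants by design.

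**Step 3. Group sizes.** Protocol Section 9.2 plans about 2000 participants in Part 2, of whom about 1700 are in the Prevention Cohort (allocation 1:1:1). The Treatment Cohort (1:1) has no stated size. The difference, 2000 − 1700 = 300, is an upper-end value, because the synopsis describes the 1700 as RT-PCR and serology negative. A cohort of 100 is an assumed lower case.

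- Prevention arm: 1700/3 = 566.7.
- Treatment Cohort 300: 150/(566.7 + 150) = 150/716.7 = 20.9% of the 700 mg column is POC-positive.
- Treatment Cohort 100: 50/616.7 = 8.1%. If the Part 2 total stays at 2000, each Prevention arm is 1900/3 = 633.3 and the share is 50/683.3 = 7.3%.

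**Step 4. Infection effect alone, no drug effect.** Assumed event risks, not from the documents: 3% in POC-negative and 6% to 10% in POC-positive participants. Pooled risk = (n₃ × 0.03 + n₆ × r)/(n₃ + n₆); the odds ratio (OR) is against 3%.

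| Treatment Cohort | r | Pooled risk | Spurious OR |
|---|---|---|---|
| 300 | 6% | (566.7 × 0.03 + 150 × 0.06)/716.7 = 3.63% | 1.22 |
| 300 | 10% | (566.7 × 0.03 + 150 × 0.10)/716.7 = 4.47% | 1.51 |
| 100 | 6% | (566.7 × 0.03 + 50 × 0.06)/616.7 = 3.24% | 1.08 |
| 100 | 10% | (566.7 × 0.03 + 50 × 0.10)/616.7 = 3.57% | 1.20 |

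With the total held at 2000, the two ORs for a cohort of 100 are 1.08 and 1.18.

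**Step 5. Follow-up effect alone.** Assumed 24-week TEAE risk 20% and constant hazard. The 12-week risk is 1 − √0.80 = 10.56%.

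- Treatment Cohort 300: (566.7 × 0.20 + 150 × 0.1056)/716.7 = 18.02%; OR against 20% = 0.88.
- Treatment Cohort 100: (566.7 × 0.20 + 50 × 0.1056)/616.7 = 19.23%; OR = 0.95.

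**Step 6. Vital signs.** The protocol schedules give non-hospitalized participants in arms 3 and 5 daily records on Days 2 to 57, that is 56, plus follow-up visits. Arm 6 has three post-baseline records (Days 8, 29 and 85). This contrast needs no assumed rate. SAP Table PYAD.6.7 uses all scheduled and unscheduled measurements for treatment-emergent abnormalities, so the chance of ever crossing a threshold depends on the schedule.

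**The case against.** The best reply is that pooling is inferred. No SAP sentence says to combine arms 3 and 6, and the three-group label may simply be Prevention Cohort text repeated across rows. The SAP recognizes the two cohorts elsewhere (Sections 4.2, 4.3 and 5.1.3), and protocol Section 3 foresees describing safety in the analysis populations as well as overall. That shows the intention was probably sound. It does not settle the analysis: the table governs by default, and Section 6.12 neither restricts nor adjusts by cohort.

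Several points about size do stand.

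- Full 24 versus 12 weeks is the largest follow-up contrast. Under SAP Section 6.1.5.2, Part 2 analyses run from a lock triggered by 56 moderate-or-worse cases and are repeated once the Evaluation Period is over. Neither lock waits for Day 169, so 0.88 and 0.95 are upper illustrations of that effect.
- Expected COVID-19 signs and events are largely exempt from AE and SAE reporting (protocol Section 10.3), which weakens the infection effect on those tables.
- The number of measurements matters mainly for treatment-emergent, shift and maximum/minimum summaries, less for by-visit change analyses.
- SAP Section 6.12.3 allows TEAEs to be reported separately by period, but only as an option. The exposure-adjusted rates in Section 6.12 are triggered by differential dropout, not by different planned follow-up, and would not remove confounding by infection.
- The hospitalization and ICU summaries in Section 6.12.5 are descriptive, and the tests in Section 6.16.2.5 use the Prevention and Treatment populations, so the pooling does not reach those tests.

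The Part 2 Treatment comparison would reveal itself as empty when run and is exploratory, so it is unlikely to mislead. It still has to be corrected.

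**Conclusion.** The concern holds. Followed as written, Table PYAD.6.1 gives a non-randomized 700 mg versus placebo comparison for Part 2 TEAEs, SAEs, laboratory values and vital signs, and a Part 2 Treatment comparison with no controls. That structural conclusion rests on the documents alone.

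The size does not. It depends on an unstated Treatment Cohort size and on assumed event risks: spurious ORs of 1.08 to 1.51 from infection, and 0.88 to 0.95 from follow-up, for cohorts of 100 to 300. The net direction is not fixed. No primary or key secondary analysis is affected, so this is something that should be fixed rather than a threat to the main efficacy conclusions.

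**What to change.** 1. Replace Part 2 Safety with two populations: Prevention-Cohort Safety (arms 3, 4 and 5; each active arm versus placebo) and Treatment-Cohort Safety (arms 6 and 7; descriptive, or active versus active).
2. Reconcile the arm and dose labels in the Part 2 rows of Table PYAD.6.1, and the Part 2 randomization sentence in SAP Section 5.1.2, with the arms table in protocol Section 9.3. Give every Part 2 arm a place.
3. In SAP Sections 6.10.3.4 to 6.10.3.6, 6.16.1.6 and 6.16.2.6, limit placebo comparisons in the Treatment populations to Part 1 Treatment, which has a randomized placebo group.

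The cost is SAP table and wording edits plus one extra set of safety tables, with no new data. Making the change before Part 2 is unblinded avoids a post hoc choice of safety comparator.

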5.4. Screen Failures

Screen failures are defined as participants who consent to participate in the clinical study but are not subsequently enrolled in the study. A minimal set of screen failure information is required to ensure transparent reporting of screen failure participants to meet the Consolidated Standards of Reporting Trials publishing requirements and to respond to queries from regulatory authorities. Minimal information includes demography, screen failure details, eligibility criteria, and any serious adverse event (SAE).

Individuals who do not meet the criteria for participation in this study (screen failure) may not be rescreened. Re-evaluation of venous access does not constitute rescreening and is allowable within the screening window.

6. Study Intervention

Study intervention is defined as any investigational intervention(s), marketed product(s), placebo, or medical device(s) intended to be administered to a study participant according to the study protocol.

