9.3. Populations for Analyses

The following populations are defined:

Population	Description
Entered	All participants who provide informed consent.
Enrolled/ITT	All participants assigned to treatment, regardless of whether they take any doses of study treatment, or if they took the correct treatment. Participants will be analyzed according to the treatment group to which they were assigned.
Facility Staff	All participants in the Enrolled/ITT population who are staff/employees of the facility.
Residents	All participants in the Enrolled/ITT population who are residents of the facility.
Part 1 Safety	All participants randomly assigned to study intervention in Part 1 and who take at least 1 dose of study intervention. Participants will be analyzed according to the intervention they actually received.
Part 2 Safety	All participants randomly assigned to study intervention in Part 2 and who take at least 1 dose of study intervention. Participants will be analyzed according to the intervention they actually received.
Part 3 Safety	All participants randomly assigned to study intervention in Part 3 and who take at least 1 dose of study intervention. Participants will be analyzed according to the intervention they actually received.
Fully Dosed	All participants in the Safety population who receive a complete infusion of study intervention.
Part 1 Prevention	All participants in the Enrolled/Intent-to-Treat population in Part 1 who are SARS-CoV-2 RT-PCR negative and serology negative at baseline.

Population	Description
Part 1 Treatment	All participants in the Enrolled/ITT population in Part 1 who are SARS-CoV-2 RT-PCR positive at baseline and serology negative.
Part 2 Prevention	All participants in the Enrolled/Intent-to-Treat population in the Prevention Cohort in Part 2 who are SARS-CoV-2 POC and RT-PCR negative and serology negative at baseline.
Part 2 Treatment	All participants in the Enrolled/ITT population in the Treatment Cohort in Part 2 who are SARS-CoV-2 POC and RT-PCR positive and serology negative at baseline.
Part 3 Treatment	All participants in the Enrolled/ITT population in Part 3 who are SARS-CoV-2 RT-PCR positive and serology negative at baseline.
Serology-Positive	All participants in the Enrolled/ITT population who are SARS-CoV-2 serology positive at baseline.
POC-Positive/RT-PCR Negative	All participants in the Enrolled/ITT population in Part 2 who are SARS-CoV-2 POC positive and RT-PCR negative at baseline.

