## 4. Study Objectives

### 4.1. Primary Objective

The primary study objective is to demonstrate superior efficacy of LY3819253 and LY3819253 in combination with LY3832479 over placebo in the prevention of COVID-19 among residents and facility staff of skilled nursing and assisted living facilities with a high risk of SARS-CoV-2 exposure.

The primary endpoint for each part of the study is the proportion of participants who experience a case of COVID-19, defined as the detection of SARS-CoV-2 by polymerase chain reaction (RT-PCR) with mild or worse disease severity in the 21 days after detection, within 8 weeks of randomization, in participants who are negative at baseline for SARS-CoV-2 RT-PCR and serology. In Part 2 of the study, participants must also test negative on a point-of-care (POC) test at baseline. Statistical hypothesis testing for the primary endpoint for each Part of the study will be conducted using a logistic regression method at the 2-sided 0.05 level.

To facilitate rapid prophylaxis and treatment of residents and facility staff, participants will be enrolled prior to assessment of baseline SARS-CoV-2 RT-PCR or serology results, thus multiple analysis populations will exist. The primary endpoint will be assessed on participants who are negative at baseline for SARS-CoV-2 RT-PCR and serology.

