### 4.2. Secondary Objectives

For Part 1, all secondary analyses will compare LY3819253 versus placebo in participants who are negative at baseline for SARS-CoV-2 RT-PCR and serology.

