#### **6.10.2.3. Fully Dosed Population**

As a sensitivity analysis, the primary and key secondary outcomes will be assessed using the Fully Dosed Population. Similar methodology, as described in Section 6.10.1 will be utilized for statistical hypothesis testing.

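### The SAP's Fully Dosed set excludes incomplete infusions only in the active arms, contrary to the protocol, and does not say that it is limited to the Prevention population

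*SAP*

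**What the plan says.** **Definition of the set.** The SAP row for Fully Dosed (Table PYAD.6.1) reads "All participants in the Safety population who receive either placebo or a complete infusion of study intervention". Protocol 9.3 reads "All participants in the Safety population who receive a complete infusion of study intervention". The protocol has no separate limb for placebo and needs none, because the opening of its Section 6 says: "Study intervention is defined as any investigational intervention(s), marketed product(s), placebo, or medical device(s) intended to be administered to a study participant". A placebo infusion is therefore a study intervention, and the protocol's completeness rule covers it.

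**Parent set.** Both definitions start from the Safety population. For Part 1 the SAP describes this as "All participants randomly assigned and who received any amount of study intervention in Part 1". It carries no RT-PCR, serology or cohort condition.

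**Use.** The SAP gives the purpose as "Used for sensitivity assessments in the event that there are patients who do not receive a complete infusion of study drug". SAP 6.10.2.3 says that "the primary and key secondary outcomes will be assessed using the Fully Dosed Population", with methods like those of 6.10.1. It does not mention the Prevention population.

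**General restriction.** SAP 4.1 states: "The primary endpoint will be assessed on participants who are negative at baseline for SARS-CoV-2 RT-PCR and serology". For Part 1, SAP 4.2 states that "all secondary analyses will compare LY3819253 versus placebo in participants who are negative at baseline for SARS-CoV-2 RT-PCR and serology". It limits the Part 2 secondary analyses in the same way, to baseline-negative members of the Prevention Cohort.

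**The concern.** A sensitivity analysis for incomplete dosing should differ from the primary analysis in one respect only: who received the full dose. The SAP wording brings in up to two other differences.

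The first is selection that depends on arm. Infusions can be cut short in any arm. Protocol 6.3 and SAP 5.3.2, for example, require the infusion to stop if the participant or an assessor is unblinded during it, whatever is in the bag. If people whose infusions stop early differ in risk, removing them from the active arms alone breaks the comparability that randomization gave.

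The second is a possible change of population. If 6.10.2.3 is programmed literally from the table, participants already infected or already seropositive at baseline enter an analysis of prevention endpoints. For infection by Day 29 (SAP 6.10.3.2), someone positive at baseline could count as an event simply by remaining positive.

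This is the only analysis the SAP specifies for incomplete infusions. If its result departed from the primary one, the reader could not tell whether dosing, one-sided exclusion or a different population was the cause.

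**Working it through.** **Inputs from the documents (Part 1).** Placebo risk 4.0% at 8 weeks, for moderate or worse COVID-19; risk ratio 0.33, so active risk 0.04 × 0.33 = 0.0132; 33 events (all SAP 5.2). 1:1 allocation (protocol 6.3). About 1700 randomized, of whom about 1300 are baseline-negative (protocol 1.1), or 650 per arm.

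**Not in the documents, so assumed over a range.** The rate of incomplete infusions and the relative risk of those affected; the RT-PCR-positive share of participants outside the Prevention population, their event rate, and the drug effect in them. No placebo rate is given for the primary endpoint (mild or worse), so the 4.0% stands in.

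**The plan's own figure.** The SAP gives no number for the Fully Dosed analysis. Its Part 1 event count can be checked with Schoenfeld's formula, D = 4(1.960 + 1.282)² / (ln θ)². With θ = 0.33, D = 34.2. With θ set to the odds ratio implied by the two risks, (0.0132/0.9868)/(0.04/0.96) = 0.321, D = 32.6, which rounds up to 33. Expected events at 1300 are 650 × (0.0400 + 0.0132) = 34.6. The inputs are coherent and are used below.

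**1. One-sided exclusion.** Let a share f of each arm have incomplete infusions, with m times the completers' risk. Risk among active completers is the active-arm risk divided by 1 + f(m − 1). The placebo arm is left whole, so

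observed RR = true RR / [1 + f(m − 1)].

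| f | m | Divisor | True RR 0.33 appears as | True RR 1.00 appears as |
|---|---|---|---|---|
| any | 1 | 1.00 | 0.330 | 1.000 |
| 1% | 2 | 1.01 | 0.327 | 0.990 |
| 2% | 3 | 1.04 | 0.317 | 0.962 |
| 5% | 3 | 1.10 | 0.300 | 0.909 |
| 5% | 5 | 1.20 | 0.275 | 0.833 |

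With 650 in the active arm, 1% to 5% is about 6.5 to 32.5 people removed. For m above 1 the shift favours the drug. Under the protocol's rule both arms are divided by the same factor and the ratio stays at 0.33, provided incompletion has the same frequency and prognosis in each arm.

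**2. Population, if 6.10.2.3 is read literally.**

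*Part 1.* 1700 − 1300 = 400 (23.5%), or 200 per arm, lie outside the baseline-negative group. This is an upper bound, because 1700 is the ITT count and the Safety set omits the undosed. Let a share s of them be RT-PCR positive with placebo event rate r and drug risk ratio R, and let the rest have no events. The arm sizes cancel:

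RR = (650 × 0.0132 + 200·s·r·R) / (650 × 0.04 + 200·s·r).

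| s | r | R = 0.5 | R = 0.7 | R = 1.0 |
|---|---|---|---|---|
| 0 | – | 0.33 | 0.33 | 0.33 |
| 25% | 40% | 18.58/46 = 0.40 | 22.58/46 = 0.49 | 28.58/46 = 0.62 |
| 50% | 40% | 28.58/66 = 0.43 | 36.58/66 = 0.55 | 48.58/66 = 0.74 |

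*Part 2.* The Part 2 Safety set covers everyone dosed in that Part, including the Treatment Cohort, which is randomized between two active arms with no placebo (protocol 6.3 and 9.3). LY3819253 700 mg is an arm in both cohorts, and the SAP's Fully Dosed row lists a single 700 mg group, so Treatment Cohort members could be counted there with no randomized placebo counterpart. Their schedule (protocol 1.3.2) has no symptoms questionnaire and a 4-week evaluation period, and SAP 6.3.2 treats missing COVID-19 status as no event. The direction of any bias in Part 2 therefore cannot be determined.

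**3. Population, if 4.1 and 4.2 govern.** No baseline-positive participant enters, and the dilution is zero.

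**The case against.** On the asymmetry, placebo is 0.9% saline. A partial saline infusion is not under-dosing, and the stated purpose of the set concerns incomplete infusion of study drug, so the exemption has an understandable motive. Protocol 7.1 also expects discontinuation of study intervention only in rare instances. Both points stand, and they explain why the numbers are small. They do not justify the rule: placebo participants are excluded under a symmetric rule to keep the groups comparable, not because they were under-dosed. The protocol already has that rule.

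On the population, SAP 4.1 and 4.2 restrict the primary and secondary endpoints to baseline-negative participants. Section 6.10.2.3 sits under additional analyses of the primary outcome and borrows the methods of 6.10.1, which names the Prevention population. On that reading Fully Dosed is only a filter. This largely stands. What remains is that 6.10.2.3 names a different set from neighbouring sections such as 6.10.2.2 and 6.10.3.1, and that the table, taken alone, yields the unrestricted set.

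A reader might infer that the analysis is in fact diluted, perhaps with a risk ratio well above 0.6. The documents do not support that. It would require 6.10.2.3 to override 4.1 and 4.2, a sizeable RT-PCR-positive group, and no drug effect in that group (R = 1.0). Protocol 2.2 and 2.3 cite interim data suggesting that treatment may lower the risk of hospitalization in mild to moderate COVID-19, so R = 1.0 is not a neutral assumption. The 4.0% is also a moderate-or-worse rate; a higher rate for the primary endpoint would shrink the dilution.

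**Conclusion.** Two defects of wording are established. The SAP's completeness rule is one-sided and conflicts with protocol 9.3, and neither the Fully Dosed definition nor SAP 6.10.2.3 states a restriction to the Prevention population.

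The first is probably small in effect: a true risk ratio of 0.33 would appear as about 0.327 to 0.275 under assumed incompletion of 1% to 5% and 2 to 5 times the risk, and would not move at equal risk. The second is an ambiguity rather than a demonstrated bias. Its effect runs from none (0.33) to substantial, depending on the RT-PCR-positive share, event rate and drug effect, none of which the documents supply.

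The primary test and the multiplicity scheme in SAP 6.5 are untouched. Nor do the documents support inferring that the primary result is at risk. This is a minor correction to a sensitivity analysis, worth making because it is cheap and nothing else in the SAP addresses incomplete infusions.

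**What to change.** 1. In SAP Table PYAD.6.1, replace the Fully Dosed definition with the rule in protocol 9.3, and say explicitly that completeness is required in every arm, placebo included. Do not narrow it to the assigned intervention: that would also remove anyone given the wrong product, which is a separate change.
2. In SAP 6.10.2.3, add a sentence such as: *This analysis is restricted to members of the relevant Part's Prevention population whose infusion, active or placebo, was complete.*

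The cost is one table row and one sentence. No new data are needed, since SAP 6.12.2 already classifies each infusion as complete or incomplete.
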